11. PHOTOGRAPHY

Photography documentation is required in this study. These standardized global and macro photos, using the Canfield system, are required to document the status of hair growth prior to, during, and after treatment with the IP. In addition, at any time during the study, at the discretion of the investigator, photographs may be taken to document the effects of treatment, AEs, or other findings during the study. The site will be provided with suggested guidelines to assist them in taking standardized photographs.

For any photographs taken of readily identifiable features (e.g., the face), an effort will be made to de-identify the photos (i.e., a masking bar over the eyes). In addition, subject identifiers (i.e., codes) will be used to identify photographs to the appropriate subject.

Note: Subjects who decline to have photographs taken during the conduct of study may not participate in the study given that photography is required. If a subject initially consents to photographs, then declines further photography, the Sponsor may use the photographs taken under consent for the purposes noted above.

Additional details and instructions regarding the standardized global and macro photography methods are provided by Canfield Scientific.

11.1 Standardized Global Photography

Standardized global photography (i.e., a vertex view and a superior view) for SSA and IGA will be performed per the SOE.

The standardized global photos taken at Visit 1/Screening will be used as the baseline photos for the IGA and SSA. If Screening photos are not adequate and re-shoot prior to Baseline was not performed, additional global photos will be taken at Baseline prior to scalp micro-dot tattoo and standardized macro photography. At subsequent visits where standardized global photography is performed, photos may not be repeated.

11.2 Standardized Macro Photography

A scalp micro-dot tattoo will be performed at Visit 2/Baseline to assist with standardized macro photography. At subsequent visits, the tattoo will be checked for fading and re-applied, if required.

Standardized macro photography will be performed per the SOE. If repeat macro photos are required, they must be taken within 7 days after the scheduled visit.

Quantitative hair measurements will include TAHC, TAHW, and TAHD which will be calculated using digital image analysis from standardized macro photos. TAHC, TAHW, and TAHD will be calculated for non-vellus and vellus/vellus-like (miniaturized) hair, separately.

12. LABORATORY TESTS

12.1 Blood Chemistry, Hematology, Urinalysis, and Cardiac Biomarkers

Blood and urine specimens will be collected per the SOE for chemistry (including lipid panel and thyroid function), hematology, urinalysis, and cardiac biomarkers. It is preferred that subjects be fasting (approximately 8 hours) for all laboratory assessments; however, if a subject arrives at the clinic without fasting for at least 8 hours, laboratory specimens may be collected as non-fasting, at the discretion of the investigator, and with the appropriate fasting status documented on the lab requisition form. However, the subject must have at least one fasting set of labs prior to treatment being administered on Visit 2/Baseline.

The following laboratory tests will be performed:

LABORATORY TESTS		
Chemistries	Hematology	Urinalysis
Albumin	Hemoglobin	Color
Alkaline phosphatase	Hematocrit	Appearance/Clarity
ALT (SGPT)	MCV	Bilirubin
AST (SGOT)	MCH	Blood
Bilirubin, total	MCHC	Glucose
Calcium	RBC (Erythrocytes)	Ketones
Carbon Dioxide §	WBC (Leucocytes)	Leukocyte Esterase
Chloride	RDW	Nitrite
Creatinine	Differential count	pH
GGT	Basophils	Protein
Glucose (fasting, preferred)	Eosinophils	Specific gravity
LDH	Lymphocytes	Urobilinogen
Phosphate	Monocytes	Microscopic analysis (if indicated)
Potassium	Neutrophils	
Protein, total	Platelets	
Sodium		
Urea (BUN)	Cardiac Biomarkers	
Uric acid	CK-MB	
Lipid Panel	Troponin T	
Cholesterol, total	NT-proBNP	
Triglycerides		
Thyroid Function		
TSH		
Total T3		
Free T4		

§ Bicarbonate may be substituted if the participating lab does not perform assay for carbon dioxide.

Sample collection, handling, labeling, and shipping should be done following the instructions provided by the relevant certified laboratory and the applicable local regulations.

The investigator must review all the subject's laboratory reports in a timely manner. **NOTE:** The investigator will initial and date each laboratory report to indicate his/her review. The investigator

will note, directly on the laboratory report, whether or not any abnormal test results are clinically significant or not clinically significant. Clinically significant laboratory abnormalities that are present at Screening and/or Baseline must be documented in the subject's medical history. In addition, the investigator must complete an appropriate AE form for any new or worsening abnormal test results that are identified as clinically significant after Baseline.

AEs that may be associated with venipuncture and that must be included in the informed consent include:

- Pain
- Bruising
- Bleeding at the puncture site
- Fainting
- Inflammation of the vein

12.2 Serology

Blood samples will be collected for serology per the SOE. Samples will be analyzed for detection of antivirus antibodies for HIV, HBsAg, or hepatitis C. The results must be negative for the subject to be enrolled.

12.3 Drug Screen

A urine drug screen will be performed per the SOE in the clinic. Urine will be screened for the following drugs (cut off in ng/mL): amphetamines (500), barbiturates (300), buprenorphine (10), benzodiazepines (300), cocaine (150), methadone metabolite (300), ecstasy (MDMA500), methamphetamine (500), methadone (300), opiates (300), oxycodone (100), phencyclidine (25), tricyclic antidepressants (1000), and tetrahydrocannabinol (50). The results must be negative for the subject to be enrolled.

12.4 Alcohol Screen

A saliva alcohol screen will be performed per the SOE in the clinic. The results must be negative for the subject to be enrolled.

12.5 Pharmacokinetic Tests

Blood samples will be collected per the SOE. At Visit 2, subjects will be dosed in the clinic and a PK blood sample will be collected before the first dose as well as 1-4 hours post-dose. At Visits 4, 6, 8, and 9, PK blood samples will be collected. These visits should be scheduled so that PK sample collection will occur 1 to 4 hours after the subject has self-applied the IP application at home. Sampling date/times will be recorded on the appropriate eCRFs. Concentrations of TDM-105795 in plasma will be determined from these samples using validated analytical methods.

The method of sample collection for PK analysis, along with specific instructions on labeling and management of these specimens, is detailed in the laboratory manual to be provided by the

laboratory vendor. The laboratory manual will also include instructions on how blood samples will be processed, stored, and transported to the analytical laboratory.

13. END OF STUDY CRITERIA

At the end of each subject's participation in the study, the investigator will complete an End of Study Disposition form for all completed and discontinued subjects.

13.1 Completion of the Study

Subjects who complete the 16-week course of treatment and complete Visit 10/EOS clinic visit as specified in this protocol will be considered to have completed the study.

13.2 Subject Discontinuation

A subject may be withdrawn from the study prior to completion for any of the following reasons:

- AEs
- Death
- Lack of efficacy⁶
- Lost to follow-up
- Non-compliance with study drug
- Physician decision
- Progressive disease⁷
- Protocol violation⁸
- Study terminated by Sponsor
- Withdrawal by subject; NOTE: if the subject decides to withdraw from the study due to an AE then it should be classified as withdrawal due to an AE
- Other (e.g., any reason that may affect the outcome of the study or safety of subjects)

If a subject withdraws from the study prematurely for any reason, the site should make every effort to have the subject return to the clinic to perform all of the required visit activities and to collect and reconcile all IPs (if applicable). If the subject will not return to the clinic, the site should make every attempt to contact the subject; otherwise the subject will be considered lost to follow-up.

When a subject is withdrawn from the study for an IP related AE (as defined in [Section 14.2](#)), when possible, the subject should be followed until resolution or stabilization of the AE.

⁶ Defined as the lack of expected or desired effect related to a therapy.

⁷ Defined as a disease process that is increasing in extent or severity.

⁸ Defined as a significant departure from processes or procedures that were required by the protocol. Violations often result in data that are not deemed evaluable for a per-protocol analysis, and may require that the subject(s) who violate the protocol be discontinued from the study.

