26. Subject has a positive screen for alcohol or drugs of abuse at Visit 1/Screening or Visit 2/Baseline.
27. Subject has signs or symptoms consistent with COVID-19 at Visit 1/Screening or Visit 2/Baseline or has been diagnosed with COVID-19 within 4 weeks of Visit 1/Screening.
28. Subject has a history of sensitivity to any of the ingredients in the IP or tattoo ink.
29. Subject is known to be noncompliant or is unlikely to comply with the requirements of the study protocol (e.g., due to alcoholism, drug dependency, mental incapacity) in the opinion of the investigator.

5.1.3 *Subject Withdrawal Criteria*

Procedures for handling subjects who are discontinued from the study are described in [Section 13.2](#). Subjects who are discontinued may be replaced at the discretion of the Sponsor.

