17. STATISTICAL CONSIDERATIONS

17.1 Estimands for Efficacy Endpoints

Treatment conditions of interest	
Condition under study: AGA in males.
 
IPs:
 
• TDM-105795 topical solution, 0.0025%• TDM-105795 topical solution, 0.02% 
Comparator Drug:
 
• TDM-105795 topical vehicle solution (Placebo)
Population	Male subjects 18-55 years of age with mild to moderate AGA
Endpoints	
The primary endpoints will be changes from Baseline in non-vellus TAHC using digital image analysis at Week 16, and the subject's evaluation of treatment benefit via the HGA questionnaire at Week 16.
 
The secondary endpoints will be:
 
1. Changes from Baseline in non-vellus TAHW using digital image analysis at Week 16.2. Changes from Baseline in non-vellus TAHD using digital image analysis at Week 16.3. The subject's evaluation of treatment benefit via the HGI questionnaire at Week 16.4. Proportion of subjects with each IGA grade at Week 16.

Population level summary	
Primary endpoints: The changes from Baseline at Week 16 in the non-vellus TAHC will be evaluated by analysis of covariance (ANCOVA) where the model includes treatment and site as factors and the baseline TAHC as the covariate. Least squares means (LSM) will be presented for pairwise comparisons of treatment groups. Descriptive statistics will be also provided by treatment group for each time point for non-vellus quantitative hair measurements.
 
The HGA will be evaluated at Week 16 descriptively (frequencies and percentages) for each assessment category by treatment group.
 
Secondary endpoints: The changes from Baseline at Week 16 with respect to non-vellus TAHW and TAHD will be evaluated by ANCOVA with treatment group and site as fixed factors, and the corresponding baseline value as the covariate. LSM will be presented for pairwise comparisons of treatment groups.
 
Each of the 3 subject-rated questions that comprise the HGI will be summarized by frequency and individual response category at Week 16 by treatment group.
 
The IGA will be summarized by frequency and individual response category at Week 16 by treatment group.

ICEs and strategies to handle ICEs	A treatment policy strategy will be employed where no ICEs will be defined. No imputation for missing data will be performed.

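### Nothing asks a subject who stops product to attend Week 16, and Section 13.2 permits study withdrawal for outcome-related reasons, so the treatment-policy strategy may lack the data it needs

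*Protocol*

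**What the plan says.** **Leaving the study.** Protocol Section 13.2 begins "A subject may be withdrawn from the study prior to completion for any of the following reasons". The list includes "Non-compliance with study drug", lack of efficacy (footnote 6: "Defined as the lack of expected or desired effect related to a therapy") and progressive disease (footnote 7: "Defined as a disease process that is increasing in extent or severity"). It does not distinguish stopping IP from leaving the study.

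**Completing the study.** Section 13.1 counts as completers "Subjects who complete the 16-week course of treatment and complete Visit 10/EOS clinic visit".

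**Data at exit.** For any premature withdrawal, Section 13.2 says "the site should make every effort to have the subject return to the clinic to perform all of the required visit activities". Footnote 1 to the Schedule of Events makes Visit 9 the early-termination visit, which includes the self-assessments, the IGA and macro photography.

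**Analysis.** Protocol Section 17.1 states "A treatment policy strategy will be employed where no ICEs will be defined", and SAP Section 8.1 says the same. The primary hair-count (TAHC) analysis is an ANCOVA at Week 16 (SAP 8.8.1.1). SAP 8.8.2.1 assigns early-termination visits to analysis visits by study day, and SAP 8.8.2.2 rules out imputing efficacy endpoints.

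**Replacement.** Section 5.1.3 adds "Subjects who are discontinued may be replaced at the discretion of the Sponsor".

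**The concern.** Under a treatment-policy strategy the Week 16 outcome counts whether or not the subject is still using IP. That requires Week 16 data from subjects who have stopped. The plan names the strategy but has no sentence that secures those data.

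The listed reasons make this more than a matter of numbers. If the disease in footnote 7 is read as the hair loss under study, progression is an unfavourable value of the endpoint itself, and lack of efficacy is close to it. Withdrawal on those grounds can make missingness at Week 16 depend on outcome, and it can do so unequally across arms. The quantities at stake are the Week 16 least squares means with their 95% CIs and the Week 16 HGA distribution, on which a proof-of-concept reading would rest. Replacement can restore the headcount, but it does not restore the missing outcomes.

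**Working it through.** **1. The plan's own figures.** There is no power, dropout or SD figure to reproduce. The sample size rests on clinical considerations (Protocol 17.2). The only check is 72 / 3 = 24 per arm, which agrees with the synopsis.

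**2. Where an early-termination visit is counted (SAP 8.8.2.1).**

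| Study day of visit | Analysis visit |
|---|---|
| 2–42 | Visit 4 (Week 4) |
| 43–70 | Visit 6 (Week 8) |
| 71–98 | Visit 8 (Week 12) |
| 99 or later | Visit 9 (Week 16) |

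Treatment runs 112 days. Days 99 to 112 are 112 − 99 + 1 = 14 days, and 14 / 112 = 12.5%. The first 98 days are 98 / 112 = 87.5%. For exits in that larger part of the treatment period, an early-termination visit made at the time does not reach the Week 16 analysis. It is kept at the earlier analysis visit, unless a nominal visit already fills that window, in which case the nominal value is used.

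**3. Tracing a subject who permanently stops IP on, say, Day 60.**
- If he is withdrawn, one visit is sought and counts as Week 8. He has no Week 16 value, nothing is imputed, and he is absent from the Week 16 ANCOVA and the Week 16 HGA.
- If he is not withdrawn, nothing prevents him from attending Visit 9, but no sentence asks him to. Even if he attends every visit, Section 13.1 does not count him as a completer.

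**4. Illustrative shift in one arm's mean.** The assumptions, none of them from the documents, are that the Week 16 change is normal, only vehicle subjects leave for worsening, and a fraction q of them leaves. If exactly the worst q leave, the observed mean rises by φ(z_q) / (1 − q) SD, where φ is the standard normal density and z_q its q-quantile. If status at withdrawal correlates ρ with the Week 16 value, multiply by ρ.

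| q | Upper bound (ρ = 1) | ρ = 0.5 |
|---|---|---|
| 5% | 0.109 SD | 0.054 SD |
| 10% | 0.195 SD | 0.097 SD |
| 20% | 0.350 SD | 0.175 SD |

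At 24 per arm, 10% is 2.4 subjects.

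**5. Net effect when both arms lose subjects.** Let m be the number of SDs by which those lost would have been worse than those observed. The bias in active minus vehicle is (q_active − q_vehicle) × m.
- Equal fractions and equal m: 0.
- 5% active, 10% vehicle, m = 1: (0.05 − 0.10) × 1 = −0.05 SD.
- 10% active, 20% vehicle, m = 1: (0.10 − 0.20) × 1 = −0.10 SD.
- 5% active, 20% vehicle, m = 1: (0.05 − 0.20) × 1 = −0.15 SD.
- Worst case, with the lowest responders always the ones lost: 0.109 − 0.195 = −0.086 SD (5% vs 10%), and 0.109 − 0.350 = −0.241 SD (5% vs 20%).

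Swapping the arms reverses the sign.

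**6. Against precision.** With 12 sites, 3 arms and 1 covariate, the residual df are 72 − 3 − 11 − 1 = 57. The 95% CI half-width for a pairwise difference is t(0.975, 57) × √(2/24) = 0.58 residual SD. With 10% loss in every arm it is about 0.61.

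**The case against.** The strongest reply is that the text is permissive and the data flow is better than it first looks. Much of this stands:

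- Section 13.2 says that subjects may be withdrawn. No threshold of worsening or non-compliance triggers exit, and the list also serves to code reasons for the disposition form in Section 13.
- A full early-termination visit is sought, so a withdrawn subject's later status is not simply discarded.
- Section 14.2 refers to adverse events that lead to IP being paused or stopped. Appendix 3 (A 3.5, A 3.6) covers stopping use for irritation, reduced frequency and drug holidays. None of these says that the subject leaves the study.
- Non-compliant subjects remain in the ITT population. Compliance is classified at 80%, and significant deviations exclude a subject only from the per-protocol population.
- Section 13.1 labels completers. It does not govern attendance or use of data.
- No formal tests are planned, and a 0.10 SD shift is small beside a half-width of about 0.6 SD.

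A reader might therefore be tempted to infer that Section 13.2 removes worsening or non-compliant subjects, that their off-product data are never collected, or that the result is an on-treatment estimate under another name. The documents support none of these. The reply still leaves the gap open: no sentence asks an off-product subject to attend Week 16. Permissive wording leaves each case to the discretion of about 12 sites without a common rule. The absence of formal tests does not protect an estimate from bias.

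**Conclusion.** The point holds as a gap between the stated strategy and the data the plan secures. Withdrawal from the study is permitted for reasons that can reflect the outcome, follow-up to Week 16 after stopping IP is not requested, early-termination data before Day 99 do not count as Week 16, and nothing is imputed. This can bias the Week 16 comparison, so it is more than missing detail and should be changed.

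The size is unknown. About 0.10 SD in the vehicle mean, with an upper bound of 0.20 SD, applies only to 10% one-sided vehicle loss of worsening subjects, with correlation 0.5 and 1 respectively. A reader might also infer that the drug effect must be understated. That follows only if vehicle loses more poor responders. Equal, similar loss gives no bias, and heavier loss of poor responders on active would overstate the effect.

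**What to change.** Leave the listed reasons, and every decision about stopping IP, as they are. In Section 13.2, add:

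- Stopping IP is not by itself withdrawal from the study.
- A subject who stops IP for any reason, unless he withdraws consent, dies or is lost to follow-up, is asked to keep the remaining scheduled visits, at minimum the Visit 9 global and macro photographs, HGA, HGI and IGA.

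Align Section 13.1 so that completing treatment and completing the study are separate statuses. Record the IP stop date and reason separately from the study exit date and reason.

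The cost is a protocol amendment and a few disposition fields. No visit or procedure is added to the existing schedule, but sites will have to follow some off-product subjects through it. The change has to be made prospectively, because Week 16 photographs that were not taken cannot be recovered in analysis.

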13.3 Study Termination

The study may be terminated by the investigator or the Sponsor. If, in the opinion of the investigator, clinical observations made during the study suggest that it may be unwise to continue, he or she may stop the study. A study termination by the investigator will be reported to the Sponsor.

In addition, a written statement fully documenting the reasons for this action will be submitted to the Sponsor by the investigator within 5 working days.

In the event that the Sponsor chooses to discontinue or terminate the study, appropriate notification will be given to the investigator.

14. ADVERSE EVENT REPORTING

Refer to the Investigator's Brochure (IB) for a list of AEs that are known to be associated with the IP(s) and/or study procedures.

14.1 Adverse Event Definitions

An **adverse event** is any untoward medical occurrence associated with the use of a drug in humans, whether or not considered related.

An AE (also referred to as an adverse experience) can be any unfavorable and unintended sign (e.g., an abnormal laboratory finding), symptom, or disease temporally associated with the use of a drug, without any judgment about causality. An AE can arise from any use of the drug (e.g., off-label use, use in combination with any drug) and from any route of administration, formulation, or dose, including an overdose.

A **suspected adverse reaction** is any AE for which there is a reasonable possibility that the drug caused the event. "Reasonable possibility" means there is evidence to suggest a causal relationship between the drug and the AE.

An **adverse reaction** is any AE caused by a drug. Adverse reactions are a subset of all suspected adverse reactions for which there is reason to conclude that the drug caused the event. A suspected adverse reaction implies a lesser degree of certainty about causality than adverse reaction, which means any AE caused by a drug. For the purposes of prescription drug labeling, the term adverse reaction means an undesirable effect, reasonably associated with the use of a drug that may occur as part of its pharmacological action or may be unpredictable in its occurrence.

An AE or suspected adverse reaction is considered "unexpected" if it is not listed in the IB or is not listed at the specificity or severity that has been observed. For example, under this definition, hepatic necrosis would be unexpected (by virtue of greater severity) if the IB referred only to elevated hepatic enzymes or hepatitis. Similarly, cerebral thromboembolism and cerebral vasculitis would be unexpected (by virtue of greater specificity) if the IB listed only cerebral

vascular accidents. "Unexpected," as used in this definition, also refers to AEs or suspected adverse reactions that are mentioned in the IB as occurring with a class of drugs or as anticipated from the pharmacological properties of the drug, but are not specifically mentioned as occurring with the particular drug under investigation.

Timely and complete reporting of all AEs assists the Sponsor and/or their designee (e.g., Therapeutics, Inc. [TI]) in identifying any untoward medical occurrence, thereby allowing:

- 1) protection of the safety of study subjects;
- 2) a greater understanding of the overall safety profile of the IP;
- 3) recognition of dose-related IP toxicity;
- 4) appropriate modification of study protocols;
- 5) improvements in study design or procedures; and
- 6) adherence to worldwide regulatory requirements.

